11.2 Statistical Analysis Plan and Methods of Analysis

A separate Statistical Analysis Plan (SAP) will be developed by the Study Statistician(s) and SSC.

Defining the early life respiratory phenotypes: Proteome, lung imaging, clinical and demographic data will be combined to examine longitudinal alterations with ANOVA (multi-comparison), generalised additive models and post-hoc analysis using Perseus/R. Both supervised and unsupervised multivariate approaches including principal component analysis (PCA), Latent Class Analysis, hierarchical cluster analysis and partial least square discriminant analysis (PLS-DA) maybe used to assess i) which clinical/protein/imaging measures tend to cluster at each time-point, ii) how background changes in protein densities, functional imaging and cardiorespiratory measures relate to different clinical treatments. Significant correlations between candidate proteins, imaging, clinical and physiological markers will be identified with permutation tests with custom R scripts written by the Study Statistician(s) and multivariate visualisations (network maps) of important clinical-imaging-protein trait interactions (assessed with canonical correlation analysis) visualised. Phenotype discovery will target two broad sub-types: 1) known and novel disease-mechanisms and 2) outcome-based signatures.

Development of a biomarker-based BPD risk (and 1 and 2 year) prediction model: We will develop a risk prediction model for BPD diagnosed at 36 weeks, based on a combination of proteins, imaging and clinical measures (minimum 7 inputs) derived within the first 7 days after birth. Model development will include several steps starting with methods for variable selection and model fitting to testing the performance and validation of models. To test measures originally significantly associated with BPD, and identify other measures that are predictive of BPD, binary logistic regression, multiple forward stepwise logistic regression, and other classification models will be evaluated with likely measures as covariates. This approach is similar to other recent studies that developed prognostic, biomarker-based models for predicting adverse outcomes in adults with respiratory problems. (34) Model performance and discrimination will then be evaluated. Internal validation with both cross-validation and bootstrapping methods to adjust for model over-optimism and bias towards inherent overestimated performance metrics will be applied. A similar strategy will be used for developing and testing risk prediction models at 1 and 2 years, which will include initial variable selection and subsequent model performance (AUC, discrimination) and validation (cross-validation) tests. We will examine several methods (e.g. growth curve trajectory) for coding repeatedly measured predictor variables that best capture developmental changes related to lung injury over time and subsequent respiratory risks. Cox proportional-hazards regression models and Kaplan-Meier survival curves will be used to further investigate and illustrate differences in BPD risk outcomes between high-risk and low-risk groups based on prognostic scores derived from BPD risk models, which will be useful to account for infants that may be lost to follow-up before 2 years.

Testing and developing alternative machine learning models of BPD risk.

While binary logistic regression is commonly used for developing risk prediction models when disease outcomes are binary yes/no, it will be important to test alternative risk prediction models that may be better able to handle high dimensional data (protein data, imaging data) and capture nonlinear relationships between variables. Some studies have shown a slight improvement in model prediction performance between logistic regression (LR) and machine learning (ML) algorithms,(37) while others have not.(38) AI methods are showing particular promise for providing advancements in areas where disease prediction is based on complex data such as lung imaging(39) or protein data.(40) Given BLUEPRINT will test whether integration of traditional BPD risk factors with protein, imaging and other data may improve prediction of BPD outcomes, it will be important to test alternative risk prediction models. We will test several commonly used ML algorithms (e.g. K-nearest neighbour, random forests, support vector machine). LR and ML models will all be internally validated and compared using the same data. Model performance will be compared with accuracy, sensitivity and specificity.

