STUDY POPULATION	
Infants born between 22+0 and 31+6 weeks' gestation admitted to a participating centre from whom prospective parental informed consent can be obtained will be considered eligible. If parental consent cannot be obtained or if lung imaging or blood sampling would compromise clinical care or well-being, the infant will be considered ineligible for participation in this study.
 
A sample size of 550 infants will allow for prediction models of BPD using up to 12 variables from the respiratory phenotype data collected in the first 7 days after birth with a C-index of 0.75 (assuming 5% lost to follow up). This sample size will have sufficient power to address the endotyping and respiratory health

	objectives of the study at 1- and 2-years corrected age, with account for anticipated loss to follow up rates.
DESCRIPTION OF SITES ENROLLING PARTICIPANTS	All Level 6 NICUs in Melbourne, Victoria (Australia) will be invited to participate (5 sites maximum).
RECRUITMENT PERIOD	Approximately 5 years after first infant enrolled.
FOLLOW-UP PERIOD	2 years, assessments at 1- and 2-years (corrected).
PARTICIPANT DURATION	2 years, corrected age from birth.

GLOSSARY OF ABBREVIATIONS

ABBREVIATION	TERM
AE	Adverse Event
ANOVA	Analysis of Variance
ANZNN	Australian and New Zealand Neonatal Network: a collaborative network which monitors and reports on the care of high-risk newborns in all Australian and New Zealand neonatal intensive care units.
BPD	Bronchopulmonary dysplasia: a form of chronic lung disease that affects preterm infants
CLD	Chronic Lung Disease
CCe	Coordinating Centre
CRF / eCRF	Case Report Form / electronic Case Report Form
CXR	Chest Radiography
DCCe	Data Coordinating Centre
DMS	Data Management System
DSMC	Data Safety Monitoring Committee
EDTA	Ethylenediaminetetraacetic acid: used as an anticoagulant in blood tubes
EIT	Electrical Impedance Tomography
EMR	Electronic Medical Record
ETT	Endotracheal Tube
FiO₂	Fraction of Inspired Oxygen
GA	Gestational age
GCP	Good Clinical Practice
HR	Heart Rate
HREC	Human Research Ethics Committee
IVH	Intraventricular Haemorrhage
LCA	Latent Class Analysis
LUS	Lung Ultrasound
LUSS	Lung Ultrasound Score

Study Name: The BLUEPRINT Study

Protocol Number: 107608

Version & date: Version 1.2, dated 9 July 2024

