3.1.2 Secondary objectives

The secondary objectives of this study are:

1. To compare the respiratory endotypes associated with different respiratory outcomes using observational data at 72 hours after birth in preterm infants born between 22+0 and 31+6 weeks' gestation.
2. To develop the first functional classification of preterm respiratory disease using a combination of clinical, lung imaging and molecular biomarkers.

3. Determine how specific early preterm endotypes relate to a diagnosis of BPD to develop a predictive modelling tool for the early diagnosis of BPD that can be used in everyday clinical practice.
4. Determine how specific early preterm endotypes relate to outcomes of the primary NICU admission, including duration of invasive mechanical ventilation and supplementary oxygen support, mortality, need for supplementary oxygen at discharge home.
5. To characterise the respiratory health of preterm infants in the first 2 years (corrected) after birth.
6. To characterise overall childhood health of preterm infants in the first 2 years (corrected) after birth.
7. To determine the relationship between initial respiratory endotype, BPD status and early childhood respiratory health at 1 and 2 years of corrected age.
8. To determine the performance of early life endotypes against a 36-week diagnosis of BPD in predicting respiratory outcomes at 1 and 2 years of corrected age.
9. To determine the relationship between LUS-derived measures of respiratory status at 14 and 28 days after birth and BPD status.
10. To determine the relationship between EIT-derived measures of respiratory status at 14 and 28 days after birth and BPD status.
11. To use plasma proteomics to identify proteins whose expression is altered in the first 7 days of life in infants who later are diagnosed with BPD.
12. To use plasma proteomics to identify expression pathways associated with specific preterm respiratory endotypes in samples obtained at 72 hours and 7 days post-birth.
13. To determine the impact of clinical interventions on the development of the respiratory phenotype.

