3.2 Outcomes

Table 3a defines the outcomes measures in relation to objectives and confounders.

Table 3a Listing objectives, exposure, outcomes and outcome measures, and confounders

PRIMARY OBJECTIVE
To comprehensively define the respiratory phenotype in the first 7 days after birth of preterm infants born between 22+0 and 31+6 weeks' gestation.

Exposure:
 
Day 7 after birth.

Outcome & outcome measure:
 
Functional endotypes defined from clinical, plasma protein and lung imaging measures using latent class analysis followed by external validation via group-based trajectory modelling.

Confounding factors:
 
Maternal and antenatal factors and management, clinical decisions regarding respiratory support (site and clinician differences in guidelines and management), preterm non-respiratory complications (such as infection, neurological disease, necrotising enterocolitis).

SECONDARY OBJECTIVES
To compare the respiratory endotypes associated with different respiratory outcomes using observational data at 72 hours after birth in preterm infants born between 22+0 and 31+6 weeks' gestation.

Outcome & outcome measure
 
Functional endotypes defined from clinical, plasma protein and lung imaging measures using latent class analysis (LCA) followed by external validation via group-based trajectory modelling.

To develop the first functional classification of preterm respiratory disease using a combination of clinical, lung imaging and molecular biomarkers.

Outcome & outcome measure
 
Temporally specific respiratory phenotypes derived from longitudinal latent class analysis of clinical, lung imaging and molecular biomarker data from all time points of the study.

To determine how specific early preterm phenotypes relate to a diagnosis of BPD and use this delineation to develop a predictive modelling tool for the early diagnosis of BPD.

Outcome & outcome measure

BPD status at 36 weeks' corrected PMA using Walsh Definition and Jensen Grade of Severity and functional endotypes determined above.
SECONDARY OBJECTIVES cont.
To determine how specific early preterm endotypes relate to outcomes of the primary NICU admission, including duration of invasive mechanical ventilation and supplementary oxygen support, mortality, need for supplementary oxygen at discharge home.
Outcome & outcome measure

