6.2.3 Clinical Data

The following data will be collected by a member of the study team from the participating infant's and their mother's medical files/records, investigative reports, and bedside monitors:

Antepartum Data: These data will be completed, and entered directly into the BLUEPRINT REDCap DMS at a suitable time following infant enrolment, including:

- Documentation of mode of consent
- Confirmation that the infant meets the eligibility criteria for the study (i.e., all of the inclusion and none of the exclusion criteria)
- Documentation of Participant Identification Number (PID#)
- Maternal medical history
- Medication history
- Demographic information of the mother and infant, including:
 - Mother's year of birth
 - Mother's race/ethnicity (if consented to provide)
 - Infant's full date of birth, time of birth, sex
- Pregnancy data, including:
 - Gestational age (in weeks/days)
 - Birth weight (g)
 - Plurality of the pregnancy
 - Mode of delivery and reason
 - Fetal Growth Restriction
 - Reason for preterm birth
 - Documentation of the use of any antenatal steroids, or other emergency antenatal/perinatal medication
 - Documentation of any adverse events and/or safety issues

Delivery Room and initial NICU Stabilisation: A delegated member of the study team will enter the following data directly into the BLUEPRINT REDCap DMS at a suitable time following infant enrolment, including:

- Time of delivery/birth
- Use of delayed cord clamping and timing
- Delivered positive end-expiratory pressure settings/level; highest and lowest and duration
- Positive Inflating Pressure levels (if used)
- Fraction of inspired oxygen (FiO₂) delivered; lowest and highest levels and duration
- Duration of delivery room stabilisation
- Intubation status
- Heart Rate (HR); lowest reading
- Oxygen Saturation (SpO₂); lowest and highest levels
- Highest modified oxygenation index (SpO₂/ FiO₂) (calculated post hoc)
- Documentation of other delivery room interventions and/or medications used
- Final respiratory settings on departure from delivery room

First week of NICU care after birth: A delegated member of the study team will enter data directly into the BLUEPRINT REDCap DMS relating to the clinical course during the first 24, 48, 72 hours and at 7 days of life, including:

- Use of supplemental oxygen, including highest level of FiO₂ in the first 24, 48, 72 hours and 7 days of life

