9 SAMPLE MANAGEMENT

9.1 Specimen & Biobanking

9.1.1 Registration of a Biobank

A biobank (named “BLUEPRINT” Biobank) will be established and allocated to the Neonatal Research Group at MCRI to securely store de-identified plasma samples derived from patients recruited within the BLUEPRINT study (2x aliquots per time-point) for a 10-year period (Biobank Registration Form [BRF] submitted for approval 28/02/2024). The BLUEPRINT Biobank will be located at the Murdoch Children’s Research Institute, within the MCRI Freezer facility (ground floor of Royal Children’s Hospital), requiring restricted card access to enter the facility. CI [name] is the allocated custodian responsible for the BLUEPRINT Biobank.

Blood samples will only be collected from enrolled infants whose parent/legal guardian have provided written informed consent for the collection of biosamples. For each infant, 2x blood samples (0.2-0.5mL) will be collected at timepoints as defined by the protocol, at 72 h (\pm 12h) and 7days (\pm 12h).

Whole blood will be processed by local site pathology departments to obtain 2x plasma aliquots per time-point, which will then be transferred into de-identified barcoded microtubes that will be stored in the BLUEPRINT Biobank.

Samples will be de-identified using a barcode system, and sample storage, distribution and destruction will be tracked using the OpenSpecimen platform (<http://openspec.mcri.edu.au>). Researchers performing data analysis on plasma samples (proteomic and statistical analyses) will be required to use de-identified data only. Samples will be re-identifiable with restricted access permitted to CI [name], Data Management Specialist [name] or delegated research staff members by the BLUEPRINT Study Coordinating Centre.

Access into the MCRI -80°C freezer facility is by swipe card only, which will limit user access. The allocated freezer for long-term storage of BLUEPRINT plasma samples is equipped with the following system controls;

- **Building Management System Alarms:** If the temperature increases $>$ -70°C, an alarm is triggered to the main Royal Children’s Hospital console, whereby facility controllers will check the freezer to ensure temperature integrity is maintained. Emergency contact (CI [name]) listed on the freezer will be notified if required.

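### The BPD and 1- and 2-year prediction models get internal validation only, which cannot show how a tool meant for everyday practice would perform at a new site

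*Protocol*

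**What the plan says.** Protocol section 11.2 states the validation of the BPD model: "Internal validation with both cross-validation and bootstrapping methods to adjust for model over-optimism and bias towards inherent overestimated performance metrics will be applied". It gives the 1- and 2-year models a similar strategy and names cross-validation for them. For the comparison of logistic regression with machine learning it says "LR and ML models will all be internally validated and compared using the same data". The resampling unit is not stated. The protocol mentions external validation only for the endotypes in section 3.2, Table 3a ("followed by external validation via group-based trajectory modelling"), not for the prediction models.

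The intended use is in section 3.1.2: "a predictive modelling tool for the early diagnosis of BPD that can be used in everyday clinical practice". Section 2.1 presents the work as relevant to neonatal intensive care internationally.

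On site and family structure:
- The synopsis says "All Level 6 NICUs in Melbourne, Victoria (Australia) will be invited to participate (5 sites maximum").
- Table 3a lists among the confounders "clinical decisions regarding respiratory support (site and clinician differences in guidelines and management").
- Section 9.1.1 says "Whole blood will be processed by local site pathology departments to obtain 2x plasma aliquots per time-point".
- Section 6.2.3 records "Plurality of the pregnancy". Section 4.4.1 admits any infant who meets the criteria, with no limit of one infant per pregnancy.

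**The concern.** Cross-validation and the bootstrap answer one question: how much of the apparent performance is overfitting in this cohort? A tool for everyday practice raises a second one: does the model hold in a unit that did not contribute data? When every site sits in both the training and the test part, pooled resampling cannot answer that.

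By the protocol's own account, site can enter both sides of the model. Respiratory support settings are collected as first-week data and differ by local practice. BPD is itself defined by respiratory support and oxygen need at 36 weeks (section 2.1). Plasma is prepared locally, and section 6.2.4.2 lists more than one ultrasound system. A model could therefore gain apparent discrimination from differences between sites, or predict the wrong average risk at a unit whose BPD rate differs. Siblings are a smaller version of the same problem.

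At stake is what the study can claim about the tool beyond the participating NICUs.

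**Working it through.** **1. The protocol's own figure.** Section 11.1 gives 500, 550 and 600 infants for 10, 11 and 12 predictors (prevalence 0.69, C-index 0.75). I took the usual pmsampsize settings, which the protocol does not state; the shrinkage criterion (0.9) is the binding one. A C-index of 0.75 converts to a Cox-Snell R² of 0.1616.

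n = P / [(0.9 − 1) × ln(1 − 0.1616/0.9)] = P / 0.01979

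This gives 506, 556 and 607, within about 1% of the protocol. Leave-one-site-out validation changes none of these.

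**2. Simulation.** The documents give no between-site variation, so the following are assumptions:
- 5 sites of about 105 infants (525/5).
- 5 clinical variables and 200 proteins, with 11 predictors chosen inside each training set; logistic regression.
- 28% of infants from multiple births; sibling correlation 0.5 (also 0.8 in one setting).
- Truth taken from 20 new sites.
- Site effects as an SD on the logit scale plus a protein shift in SD units.

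To read the scale: an infant with 69% risk at an average site (logit 0.80) would have, at a site one SD below or above, 62% or 75% (SD 0.3), 57% or 79% (SD 0.5), and 50% or 83% (SD 0.8).

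Risk error is the mean absolute gap between observed and average predicted risk.

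Signal near the planned C-index (150 replicates):

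| Site SD / protein shift | Pooled CV AUC | Leave-one-site-out AUC | New-site AUC | Pooled minus new | Risk error, pooled | Risk error, new site |
|---|---|---|---|---|---|---|
| 0 / 0 | 0.739 | 0.733 | 0.745 | −0.006 | 0.003 | 0.038 |
| 0.3 / 0.3 | 0.733 | 0.731 | 0.742 | −0.009 | 0.003 | 0.067 |
| 0.5 / 0.5 | 0.730 | 0.726 | 0.733 | −0.003 | 0.003 | 0.094 |
| 0.8 / 1.0 | 0.743 | 0.725 | 0.725 | +0.018 | 0.002 | 0.134 |

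Weaker signal (60 replicates):

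| Site SD / protein shift | Pooled CV AUC | Leave-one-site-out AUC | New-site AUC | Pooled minus new | Risk error, leave-one-site-out | Risk error, new site |
|---|---|---|---|---|---|---|
| 0 / 0 | 0.619 | 0.617 | 0.626 | −0.007 | 0.040 | 0.041 |
| 0.3 / 0.3 | 0.624 | 0.620 | 0.629 | −0.005 | 0.069 | 0.069 |
| 0.5 / 0.5 | 0.639 | 0.616 | 0.618 | +0.021 | 0.103 | 0.099 |
| 0.8 / 1.0 | 0.681 | 0.632 | 0.630 | +0.051 | 0.137 | 0.145 |

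Monte Carlo standard errors of the AUCs are 0.001 to 0.006. Three readings:
- The new-site and leave-one-site-out AUCs are averaged within site, while the pooled AUC also credits risk differences between sites. Part of the positive gaps is that credit.
- The pooled risk error covers the whole cohort, so the fair baseline for a site of about 105 is the no-effect row (0.038), which is sampling noise.
- In the second table the leave-one-site-out risk error tracks the new-site error closely.

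**3. Siblings.** Infant-level minus pregnancy-level cross-validation, with the signal near the planned C-index, gave 0.001 to 0.003 in AUC for logistic regression and 0.004 to 0.009 for K-nearest neighbour.

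**4. Precision of the remedy.** With five equal sites, each model trains on 525 × 4/5 = 420 infants, below the protocol's 500 for 10 predictors. A held-out site has about 105 × 0.69 = 72 infants with BPD and 33 without. By the Hanley-McNeil formula at AUC 0.75, SE = √[(0.1875 + 71 × 0.0375 + 32 × 0.0804) / (72 × 33)] = 0.048, or about ±0.09 at 95%. The observed BPD rate has SE √(0.69 × 0.31/105) = 0.045, also about ±0.09.

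The bootstrap was not simulated, nor was the new-site performance of machine-learning models.

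**The case against.** The strongest reply is that nothing in section 11.2 is misstated. It calls its procedure internal validation, gives it the right purpose, and claims no figure for a new site. A separate SAP is announced, and fold construction is ordinary SAP content. That stands as far as resampling detail goes: a reader might infer that individual infants are resampled with no grouping, but the protocol does not say so. The point here rests on what section 11.2 does commit to, internal validation, set against the stated use.

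There is also text that limits site effects: common laboratory manuals and mass spectrometry at one institute (sections 6.2.5 and 9.1.2), blinded re-reading of ultrasound (8.3.2), central cleaning and quality checks of EIT files (8.3.3), and imaging competency checks (8.3.4). These may shrink a site signature in proteins and images. They do not touch differences in respiratory management or in BPD rate.

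Finally, leave-one-site-out with five sites is imprecise, and its training sets are smaller than the final model's. That stands, and is why it should sit beside the bootstrap-corrected figure rather than replace it as the headline.

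**Conclusion.** The point holds in a limited form. The planned validation can describe performance within the participating NICUs and cannot show transport to another. It can overstate AUC by about 0.02 to 0.05 when between-site variation is large, or moderate with a weaker signal. With absent-to-moderate site effects and an AUC near 0.75 the check found no overstatement. The steadier loss is calibration, which pooled validation would not reveal. All sizes rest on assumed site and protein effects.

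Three stronger readings are tempting and not supported:
- That new-site performance will be overstated: size and even direction depend on between-site variation that the documents do not give.
- That sibling leakage is important: it was under 0.01 AUC.
- That the plan favours machine learning over logistic regression: this was not tested.

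**What to change.** In section 11.2, for the BPD, 1-year and 2-year models and for both logistic and machine-learning versions:
- Keep the bootstrap-corrected estimate as the figure for same-site performance.
- Report beside it leave-one-site-out (internal-external) discrimination and calibration for each held-out site, with intervals, repeating variable selection in each training set.
- Keep all infants of one pregnancy in the same fold or bootstrap draw. This needs a link between siblings; add one if the Data Management Plan does not already hold it.
- Describe the result as internally validated development for the participating sites unless an external cohort is used.

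The cost is analysis code, wording and possibly one linking field, with no new infants or measurements. The downside is five imprecise site estimates (fewer if fewer sites join), each from a model trained on about 420 infants if sites are equal, and possibly a less favourable reported performance.

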11 STATISTICAL METHODS

11.1 Sample Size Estimation

The sample size for BLUEPRINT is designed to address the robustness of early respiratory phenotypes identified predicting BPD. The prevalence of survival with BPD within the ANZNN is 0.69. Based on the R package *pmsampsize* version 1.1.3 described by Riley et al in “*Calculating the sample size required for developing a clinical prediction model*”,⁽³⁶⁾ we estimated that the following sample size will be required to develop a clinical risk prediction model with BPD (yes/no) as the outcome: assuming a BPD prevalence of 0.69 (69%; all grades) and a moderate C-index of 0.75 is achievable (latest estimates from PRELIM manuscript support this) with a binary logistic regression prediction model with BPD (yes/no) as the outcome, a minimum sample size of 500, 550 and 600 infants was estimated based on 10, 11 or 12 predictor variables respectively (from any domain of clinical, imaging and protein data). We estimate that the predictive model developed in BLUEPRINT may have up to 10-12 predictor variables which is partly based on the latest PRELIM manuscript where several basic clinical covariates (e.g. gender, gestational age) and only single proteins were included (given the limited sample size in PRELIM), however there were multiple proteins that were significantly correlated with BPD and there will be additional clinical covariates and other model terms (interactions, non-linear terms, which are counted as additional predictor variables terms in the *pmsampsize* sample size estimation) that will likely be critical to include in the BLUEPRINT study in order to achieve high performing predictive models.

The calculation above derived from the *pmsampsize* R package considers multiple criteria to arrive at an appropriate sample size that ensures precise predictions, minimises prediction errors and model overfitting/optimism, and allows for sufficient stratification by factors known to exert a strong signal on neonatal outcomes (e.g. gestational age/weight, sex and intubation in first 10 days).

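### Section 11.2 places variable selection before validation; followed literally, the validated AUC keeps the selection optimism that validation is meant to remove

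*Protocol*

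**What the plan says.** Section 11.2 of the Protocol describes the BPD prediction model in stages: "Model development will include several steps starting with methods for variable selection and model fitting to testing the performance and validation of models". Among the methods to be evaluated is "multiple forward stepwise logistic regression". The stated role of validation follows: "Internal validation with both cross-validation and bootstrapping methods to adjust for model over-optimism". The section then turns to the later outcomes: "A similar strategy will be used for developing and testing risk prediction models at 1 and 2 years". That work is to include "initial variable selection and subsequent model performance (AUC, discrimination) and validation (cross-validation) tests". The choice among several ways of coding repeatedly measured predictors is also left to be examined in the data.

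On model size, section 11.2 asks for "minimum 7 inputs", and section 11.1 says the model "may have up to 10-12 predictor variables". Neither section says how many candidate variables these are drawn from. Section 2.1 describes the group's proteomic method as untargeted, and imaging and clinical measures are added to it. Section 11.2 also announces a separate SAP, which is not available here.

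**The concern.** Cross-validation gives an honest AUC only if the held-out children played no part in building the model. If the outcomes of all children decide which variables enter, each held-out fold has already influenced the variable list. Refitting coefficients without that fold does not undo this. Bootstrapping an already selected set has the same weakness. Forward stepwise selection, univariate screening and choosing the best-performing coding of a repeated measure are all steps of this kind.

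At stake is the credibility of the reported discrimination. One of the study aims (section 2.3) is to produce predictive tools for BPD and for respiratory health in the first 2 years. With a large candidate pool, an AUC produced by selection alone could pass for a useful model.

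**Working it through.** **1. The plan's own figures.** The protocol states no validated AUC. It does state sample sizes of 500, 550 and 600 for 10, 11 and 12 predictor terms (section 11.1; prevalence 0.69, C-index 0.75). Converting these two inputs by simulation gives a Cox-Snell R² of 0.163. The shrinkage criterion is n = P / [(S − 1) · ln(1 − R²/S)] with S = 0.9. Here ln(1 − 0.163/0.9) ≈ −0.1998, so n ≈ P / 0.01998, which gives 501, 551 and 601. The other two criteria are smaller (at most 304 and 329). The stated sizes are reproduced. They count the terms in the model and do not address a search over a larger pool.

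**2. Children available at 2 years.** Section 11.1 gives 400-450. Check: 550 × 0.93 (7% mortality) × 0.80 (retention) = 409. The midpoint of the stated range is 425.

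**3. Null simulation.** Markers are standard normal and unrelated to a binary outcome. The k markers with the largest |Σ zᵢ(yᵢ − ȳ)| are kept, a logistic model is fitted, and the AUC is averaged over 10 folds. Selection is done either once on all children or again in each training set. The true AUC is 0.50.

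Inputs from the protocol: n = 400 to 450, and k = 7 to 12. Assumed: event rate 0.2, 0.3 or 0.5, and 12 to 1000 candidates. There were 60 replicates per setting (30 for 1000 candidates).

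Mean AUC with selection first, n = 400, event rate 0.3:

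| Candidates | 7 kept | 12 kept |
|---|---|---|
| 12 | 0.54 | 0.50 |
| 20 | 0.57 | 0.55 |
| 50 | 0.61 | 0.61 |
| 100 | 0.64 | 0.66 |
| 300 | 0.68 | 0.71 |
| 1000 | 0.70 | 0.75 |

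Across event rates 0.2 to 0.5 at n = 400, the ranges are 0.61-0.64 (50 candidates), 0.63-0.69 (100), 0.67-0.73 (300) and 0.70-0.77 (1000). Results at n = 450 are about the same. With selection inside the folds, the mean is 0.48-0.52 in every setting.

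**4. Central case, with correlation.** With n = 425, event rate 0.3, 10 kept and independent markers, selection first gives 0.56, 0.61, 0.65, 0.69 and 0.73 for 20, 50, 100, 300 and 1000 candidates. With blocks of correlated markers, which act like fewer candidates, the values are lower: about 0.51 at 20, 0.60 at 100 and 0.70 at 1000. With selection inside the folds it is 0.49-0.51. The excess over 0.50 is therefore 0.01-0.06 at 20 candidates, 0.10-0.15 at 100 and 0.20-0.23 at 1000.

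Top-k univariate selection stands in for forward stepwise selection, so these figures show the scale of the effect and are not forecasts.

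**The case against.** The best defence is that section 11.2 lists stages of work and does not specify a resampling algorithm. A pipeline that repeats selection in each fold could be summarised in the same words, the paragraph says validation is there to correct over-optimism, and the announced SAP may give the detail. Part of this stands: nowhere does the protocol say that selection stays outside the folds, and a reader who infers that it does goes beyond the text. But the protocol does state a sequence, and an SAP that follows it literally would not achieve the paragraph's own purpose.

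Three further readings are tempting and not supported.

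- **That only the 1- and 2-year models are exposed, because bootstrapping is named only for BPD.** The BPD model has the same stage order, the later models are tied to it as a similar strategy, and bootstrapping after selection leaks in the same way.
- **That the AUC must be well above 0.5.** This depends on a candidate count the protocol does not give. The excess is nil when 12 are kept from 12, and small with 20. Section 11.1 also points to some predictors suggested by earlier work, and candidates fixed in advance from outside data do not leak.
- **That the comparison with BPD is tilted.** The objective is "To determine the performance of early life endotypes against a 36-week diagnosis of BPD in predicting respiratory outcomes at 1 and 2 years" (section 3.1.2). Table 3a defines the endotypes by latent class analysis, which need not use the 1- or 2-year outcome. No section says that the risk model's AUC is the quantity set against BPD. Section 11.2 does allow signatures defined by outcome, so the link is possible, but it is an inference.

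**Conclusion.** The point holds as a defect in the stated order of work, for the BPD and the 1- and 2-year models alike. Taken literally and with outcome-guided selection in all children, the described validation leaves selection optimism in the reported AUC. Under the central assumptions (425 children, 30% events, 10 noise markers kept), that AUC is about 0.51-0.56 with 20 candidates, 0.60-0.65 with 100 and 0.70-0.73 with 1000, against about 0.50 with nested selection. Event rate, candidate counts and correlation structure are assumed. An untargeted proteome makes a large pool plausible, but the protocol does not confirm one. The documents do not show that the endotype comparison with BPD is biased; endotypes from latent class analysis that does not use the outcome are unaffected.

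**What to change.** Reword section 11.2, and carry the wording into the SAP, so that every step guided by the outcome is repeated within each cross-validation fold or bootstrap sample. This covers screening, stepwise selection and the choice of coding for repeated measures, for the BPD model and the 1- and 2-year models. If a model selected in this way, or a signature defined by outcome, is later compared with the 36-week BPD diagnosis, make the comparison on the same held-out children.

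The cost is a few sentences, more computing time and lower reported AUCs. No extra data or infants are needed.
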